Visit 4: All procedures as in visit 2 will be performed again, including dietary recall, targeted physical exam, and sample collection. All subjects will also get another oral FMT/placebo dose of 5 capsules each depending on their original assignment. All subjects in the study will get this intervention unless (a) they refuse the intervention (b) have undergone a liver transplant or have died/discharged to hospice (c) developed an infection or an SAE that was adjudicated to be related to FMT in the interim or (d) are currently undergoing antibiotic therapy for an infection that is not related to FMT.

For those who are infected due to an FMT-unrelated infection, we will approach the patients 2 days after the completion of the assigned antibiotic course. For those initiated on SBP (Spontaneous Bacterial Peritonitis) prophylaxis, we will provide the intervention after the initial SBP episode is treated. This may require delaying the intervention from day 30 to up to day 45 but this will still be counted as the second FMT.

All other subjects will be given the intervention and the blind will still be maintained. The brain function tests and QOL will be performed again. Groups 1 and 2 will get active FMT and groups 3 and 4 will get placebo FMT. No enemas will be given. The subjects will then be sent home.

Follow-up visits every month: The subjects will be followed monthly in person, or by phone or videoconference at Months 3, 4, 5 to evaluate dietary and medication changes and for safety analysis (hospitalizations, AEs or SAEs), targeted physical exam and for collection of samples at each study clinic visit. Mail-in kits for collection of stool, and urine will be provided along with instructions for use if visit is performed remotely. We will also perform the cognitive tests and QOL assessment at one month post-second intervention and at 6 months. We will continue to follow every patient for 6 months regardless of whether they developed an SAE or hospitalization in between. Only reasons not to follow them up for 6 months would be death, liver transplantation or patient withdrawal of consent.

End-of-Study visit: Per FDA mandates for FMT studies, we will see the patients at six months and we will evaluate AEs, interim hospitalizations, dietary recall, and perform targeted physical exam, QOL and brain function studies, and collect serum, and stool again. At this point the participation of the patient will end.

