Brain function: These will be administered at visit 1, visit 4 (one month after the second FMT), and end-of-study by [name] and the coordinator/research assistant. Two validated testing strategies, Psychometric Hepatic Encephalopathy Score (PHES) and EncephalApp Stroop Test, which have norms for the Virginia population will be used¹⁸. The PI and his team are well-published in this field and have been administering these for several years to cirrhotic patients. Both these tests showed benefit in the FMT enema trial published by our group in HE¹⁰. PHES is a recommended battery that defines brain dysfunction in cirrhosis¹⁹. It consists of 5 paper and pencil tests (number connection tests A and B, digit symbol test, line tracing test and serial dotting tests), which form a composite score of standard deviations below an age/education-matched community healthy population. This gives a score ranging between -15 and +4. In addition to this continuous score, covert hepatic encephalopathy can be diagnosed with a score <-4 for our population¹⁸. This test battery takes 15 minutes to complete. EncephalApp Stroop^{18, 20} is a freely available computerized test which consists of an easier "Off" state and a more difficult "On" state. The OffTime+OnTime is the output, which is the time taken to complete 5 correct runs in the Off and On states. The output here can be continuous (seconds in the

OffTime+OnTime) or covert hepatic encephalopathy percentage based on local norms¹⁸. This takes 5-7 minutes to complete.

Quality of Life: This will also be administered at Visit 1, Visit 4, one month after the second FMT, and End-of-Study visit. The Sickness Impact Profile (SIP)²¹ is a validated profile for QOL in cirrhosis that the PI and his team have had several years of published experience²²⁻²⁴. SIP consists of 136 questions that pertain to any issues that patients have experienced in the last 24 hours. It has a composite score, two dimensions (physical and psycho-social) and twelve individual domains that are calculated based on norms. A higher score indicates a worse quality of life. This gives only a continuous score as the output. A copy is shown in the Appendix. [name] and the coordinator/research assistant will perform these.

Endpoints and Plan of Analysis:

Primary Endpoint: FMT-related SAEs including HE recurrence within 6 months

Secondary Endpoints (details below):

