1. Study procedure-related adverse events from enema (e.g. perforation, bleeding, etc.)

- 2. FMT material-related adverse events (e.g. transmissible infection, allergic reaction)
- 3. Capsule ingestion-related adverse events (pill-associated dysphagia)

4. Short-term safety: Both solicited and unsolicited adverse events will be recorded by, clinical assessment at all in-person visits. The subjects will have the ability to telephone the study team at any point during the study.

5. Long-term safety: follow-up monthly till 6 months to evaluate for SAEs (listed below).

Solicited AEs throughout the trial will be

- (a) fever:
- (b) diarrhea
- (c) vomiting
- (d) constipation
- (e) GI bleeding
- (f) abdominal cramping and pain
- (g) Development of HE (confusion/altered mental status):
- (h) Development of infections, specifically spontaneous bacterial peritonitis
- (i) New onset or significant worsening of chronic medical conditions
- (j) New potentially transmitted infections

We do not expect the infections to occur at a higher rate than the natural history of cirrhosis at this stage. This is borne out by our enema study, in which the FMT group had no infections. Also, a nasojejunal study performed by Phillip et al in severe alcoholic hepatitis, whose MELD scores were much higher than our proposed patients, did not reveal a poor safety profile. We will monitor for all infections and specifically for spontaneous bacterial peritonitis (SBP).

All safety assessments in FMT will be compared to placebo groups given the advanced nature of the cirrhosis and the association of several of these symptoms in the natural history of the disease

Stop-points or reportable adverse events

Any hospitalization or event that is life-threatening will be deemed a serious adverse event in the FMT group and reported to the IRB, FDA, DMC and Molecular and Cellular Therapeutics (GMP) facility at the University of Minnesota within 72 hours (per usual protocol).

This will include the development of an infection that is gut-based/not gut-based:

Gut-Related

- Spontaneous Bacterial peritonitis
- Infectious diarrheal illnesses

Others

- UTI
- Respiratory
- Skin/soft-tissue
- Bacteremia

Overall Study Halting Rules

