- any cause including bleeding, nausea, vomiting, or other GI conditions
- (5) increase in MELD score by 8 or more
- (6) Increase in AST, ALT or Alkaline phosphatase to 10X ULN
- (7) Non-elective Hospitalization

Even if the subject is withdrawn before 30 days, they will still be followed till 6 months for safety.

Health risks (please see adverse events table attached):

Adverse events will be both for the FMT material, placebo as well as for the procedures. These risks are listed in the Risk Section of the informed consent.

These possible adverse events will be:

- (a) Fever: yes or no answer with grading based on actual temperature on examination
- (b) diarrhea (will be asked to grade them from 0-4 compared to baseline)
- (c) abdominal cramping and pain (will be asked to grade them from 0-4 compared to baseline)
- (d) vomiting (will be asked to grade them from 0-4 compared to baseline)
- (e) Development of HE (Altered mental status) in every group: will be monitored by clinical examination through the West-Haven Criteria²⁵. We will be closely monitoring all subjects for this development, including a clinical examination by a gastroenterologist at every visit.

(f) Development of infections specifically spontaneous bacterial peritonitis -Fever will be reconfirmed by measuring by the study nurse and if it is confirmed, a detailed investigation into the cause of the fever will be performed as part of standard clinical care and the patient will be withdrawn from the study.

-Vomiting, constipation, GI bleeding, abdominal cramps and diarrhea: If the patient's diarrhea and abdominal cramps change in a magnitude of 3 over their baseline values per the AE chart (patients with cirrhosis often have these symptoms at baseline), they will be withdrawn from the study.

-Infections that occur in the FMT group will be thoroughly investigated according to standard clinical care to prove whether they were associated with the FMT.

Adverse Event Grading Chart

 Volunteer Study ID:
 Date:
 Time:

 Study Start Date:
 Current Visit number:

*Volunteer's responses will be marked on grading sheet by circling the appropriate grade or indicating no symptoms.

PARAMETER COMPARED TO BASELINE	GRADE 1 MILD	GRADE 2 MODERATE	GRADE 3 SEVERE	GRADE 4 POTENTIALLY LIFE-THREATENING
ESTIMATING SEVERITY	(GRADE		•	•

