Suspected adverse reaction means any adverse event for which there is a reasonable possibility that FMT caused the adverse event. For the purposes of IND safety reporting, 'reasonable possibility' means there is evidence to suggest a causal relationship between FMT and the adverse event. A suspected adverse reaction implies a lesser degree of certainty about causality than adverse reaction, which means any adverse event caused by a therapy.

6. Unexpected

An adverse event or suspected adverse reaction is considered "unexpected" if it is not listed in the Investigator brochure or is not listed at the specificity or severity that has been observed; or is not consistent with the risk information described in the general investigational plan or elsewhere in the current application.

Solicited Adverse Events

According to the attached Adverse Event Grading Chart

Monitoring of Adverse Events

Each subject will be monitored for the occurrence of AEs, including SAEs. Each subject will be followed for safety monitoring at each follow-up interval and at the 6-month phone call

- Subjects will be questioned regarding stool patterns, abdominal pain, fevers, and subjective well-being. Subjects will be questioned about the possible occurrence of adverse events in a generalized way, such as, "How have you been feeling since your last visit?" Subsequent solicited questions and relevant details will be asked if there is a positive response. Site Investigators will be contacted by study representative if there is a suspected or reported AE
- Subjects having AEs will be monitored with relevant clinical assessments and laboratory tests, as determined by the site Investigator
- AEs, actions taken as a result of AEs, and follow-up results will be recorded as well as in the subject's source documentation. Follow-up laboratory results should be filed with the subject's source documentation
- Subjects will be seen every month till 6 months post-enrollment to record any SAEs, new onset of potentially transmitted infections, new medical conditions, or changes in pre-existing medical conditions (New onset or significant worsening of chronic medical conditions including, but not limited to, autoimmune diseases, inflammatory bowel diseases, metabolic syndrome, cardiovascular disorders, and neuropsychiatric disorders.)

Assessment of Adverse Events

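### Months 3 to 5 may be remote, so the HE examination and all blood measures can be missing at up to three of the five monthly contacts after the second dose; Month 6 mode and samples are stated inconsistently

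*Combined protocol and SAP*

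**What the plan says.** All references are to the combined protocol and SAP.

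- **Endpoint** (Endpoints and Plan of Analysis): "Primary Endpoint: FMT-related SAEs including HE recurrence within 6 months".
- **How HE is found** (Health risks, item (e)): it "will be monitored by clinical examination through the West-Haven Criteria", and "We will be closely monitoring all subjects for this development, including a clinical examination by a gastroenterologist at every visit". The Adverse Event Grading Chart makes asterixis part of grades 2 and 3 and its absence part of grade 1.
- **Follow-up mode** (Procedures, Follow-up visits every month): "The subjects will be followed monthly in person, or by phone or videoconference at Months 3, 4, 5". Targeted examination and sample collection are tied there to clinic visits. For the rest, "Mail-in kits for collection of stool, and urine will be provided along with instructions for use if visit is performed remotely". Cognitive and quality-of-life testing is also due one month after the second dose and at 6 months.
- **Month 6**: the End-of-Study visit paragraph has patients seen, and staff "perform targeted physical exam, QOL and brain function studies, and collect serum, and stool again". Monitoring of Adverse Events says instead: "Each subject will be followed for safety monitoring at each follow-up interval and at the 6-month phone call". A later bullet in that same section has subjects seen monthly up to 6 months.
- **Samples** (list following Duration of Follow-up after FMT): stool; blood with CBC, metabolic panel, LFTs, INR and endotoxin; and urine, at baseline and at the specified visits.

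**The concern.** An audio call cannot elicit asterixis, so it cannot apply the chart's own boundary between grades 1 and 2. The plan describes no substitute HE assessment for remote contacts. Milder HE could be missed, or graded without examination, depending on how the contact was held, and the plan does not say that contact mode is recorded. In a trial whose primary aim is safety, missed events favour a conclusion of no signal.

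The laboratory side has the same weakness. WBC, MELD, AST, ALT and alkaline phosphatase are graded events, and they appear in the individual halting rules. None can be measured from mailed stool and urine. An absence of laboratory events in the later months could partly reflect an absence of measurements.

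**Working it through.** **1. Contacts after the second dose.** The second dose is given at Visit 4 (day 30, with delay allowed to day 45). Monthly contacts then run from Month 2 to Month 6, which makes 5.

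| Contact | Mode allowed | Examination | Blood |
|---|---|---|---|
| Month 2 | In person by implication: not among the remote months, and cognitive tests (including paper-and-pencil PHES) fall due one month after the dose | Not itemised | Not itemised |
| Months 3, 4, 5 | In person, phone or video | Only if a clinic visit | Only if a clinic visit |
| Month 6 | In person (End-of-Study visit) or phone (Monitoring of Adverse Events) | Targeted, if seen | Serum, if seen |

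- Contacts that may lack both examination and blood: 3 of 5.
- In-person contacts left under the Procedures text: 5 − 3 = 2 (Months 2 and 6).
- If the phone-call wording governed Month 6: 2 − 1 = 1 (Month 2).

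**2. Gap between blood draws with Months 3 to 5 all remote.** This assumes that blood is drawn one month (30 days) after the second dose and again at about day 180.

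- Dose on day 30: draw on day 60; gap 180 − 60 = 120 days.
- Dose on day 45: draw on day 75; gap 180 − 75 = 105 days.

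**3. Month 6 samples.** The End-of-Study paragraph names serum and stool. The general list names blood with CBC and INR, plus urine. The first does not mention urine, CBC or INR; the second covers all three if the End-of-Study visit counts as one of the specified visits. Urinary metabolomics is secondary endpoint 5.

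**4. Does non-admitted HE matter?** The Statistical analysis paragraph lists hospitalizations and HE episodes as separate outcomes. Item (4) of the individual halting rules names overt HE alongside hospitalization under SAE development. Both suggest that HE without admission is meant to be noticed.

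**5. Sample size.** The plan's power figures concern hospitalization, not HE. The test is not stated. A four-group chi-square (3 df, α = 0.05) with rates 0.80, 0.30, 0.30 and 0.10 comes close. The mean rate is 0.375, and the noncentrality is n × Σ(p − 0.375)² / (0.375 × 0.625) = n × 0.2675 / 0.234375 = 1.141n.

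- n = 25: 99.75% (plan: 100%)
- n = 20: 98.8% (plan: 98%)
- n = 15: 94.9% (plan: 94%)

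Hospitalization can be ascertained by phone, so nothing here changes these figures.

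**The case against.** The strongest reply is that remote contact is optional and confined to Months 3 to 5, that Month 2 is in person by implication, and that the dedicated End-of-Study paragraph provides examination, serum, stool and cognitive testing. All of this stands. A reader might infer that examination and blood are simply not delivered after the second dose; the documents do not support that. The phone-call phrase is a conflict to settle and does not show that the visit was dropped.

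A reader might also infer that no CBC or INR need be drawn after Visit 4, or that 6-month urine has no provision. That goes too far. The general sample list can be read as supplying these at every specified visit, the Laboratory section says the relevant values will be followed, and endpoint 5 sets no 6-month timepoint. Figure 1, the visit overview, was not in the text available for this check and may say more.

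Nor does the sentence "Both solicited and unsolicited adverse events will be recorded by, clinical assessment at all in-person visits" confine adverse-event recording to clinic visits. It stands under short-term safety, and the follow-up paragraph collects hospitalizations, AEs and SAEs at monthly contacts, remote ones included.

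Finally, HE that leads to admission, threatens life or is fatal can be learned of by phone, and confusion can be reported by history. Whether non-admitted HE counts toward an endpoint worded around FMT-related SAEs is a separate question of definition. This narrows the exposure without removing it: the every-visit examination and the remote option still cannot both be followed.

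**Conclusion.** The point holds in a limited form. Three conflicts stand: an HE examination promised at every visit against remote contact at Months 3 to 5, laboratory safety grading against contacts with no route for blood, and an in-person Month 6 against a phone call. The Month 6 sample wording also needs aligning with the general list.

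The size is up to three of five post-dose contacts without examination or blood. The 105 to 120 day interval between draws applies only if all three are remote and Month 2 blood is actually taken. How many patients would be followed remotely is not stated, so the number of missed HE episodes cannot be estimated.

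A reader might go on to infer bias between arms. The documents do not show it: the trial is double-blind and the remote option is open to every group. What is shown is ascertainment that can vary with contact mode, mainly for HE that does not lead to admission.

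**What to change.** 1. Reconcile Monitoring of Adverse Events with the End-of-Study visit paragraph so that Month 6 is the in-person End-of-Study visit throughout.
2. Align the End-of-Study samples with the general sample list (stool, urine, and blood with CBC, metabolic panel, LFTs, INR and endotoxin). State that the same blood panel and the examination are done at the assessment one month after the second dose.
3. Reconcile the follow-up paragraph with Health risks item (e). Specify one fixed mental-status assessment for HE at any remote Month 3 to 5 contact, by video where possible, with the in-person examination when HE is suspected.
4. Record the mode of every contact and check HE recurrence by mode in the analysis.

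The remote option is kept. The cost is protocol wording, a few minutes per remote contact, one blood draw and one urine sample at visits already planned, and an occasional extra in-person visit.

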The primary aim is: To evaluate the safety and tolerability of fecal transplant through rectal and oral capsular routes in cirrhosis and HE from a liver disease and symptom standpoint using analysis of serious adverse events, especially HE recurrence, in a placebo-controlled trial.

Secondary aims are between the groups:

- 1. Safety and tolerability of FMT compared to placebo
 - a. Frequency, severity and relatedness of solicited and unsolicited AEs through day 30
 - b. Occurrence of new potentially transmitted infections through six-months post FMT
 - c. Occurrence of new onset or significant worsening of chronic medical conditions post-FMT
- 2. To define the changes in microbiota composition and function of the stool microbiota after FMT compared to pre-FMT baseline and donor compared to placebo

- 3. To evaluate changes in systemic inflammatory cytokines and endotoxin, quality of life and cognitive function compared to pre-FMT baseline and compared to placebo
- 4. To determine occurrence of new onset or significant worsening of chronic medical conditions through six months post-FMT and compared to placebo
- 5. To evaluate the changes in the microbiota after the second oral FMT vs. placebo compared to baseline values

Inclusion/Exclusion Criteria:

Inclusion criteria:

- A. Cirrhosis diagnosed by either of the following in a patient with chronic liver disease
 - a. Liver Biopsy
 - b. Radiologic evidence of varices, cirrhosis or portal hypertension
 - c. Laboratory evidence of platelet count <100,000 or AST/ALT ratio>1
 - d. Endoscopic evidence of varices or portal gastropathy
 - e. Fibroscan values suggestive of cirrhosis
- B. On treatment for hepatic encephalopathy (patient can be on lactulose and rifaximin)
- C. Age: at least 21 years of age
- D. Able to give written, informed consent (demonstrated by mini-mental status exam>25 at the time of consenting)
- E. Women of child bearing potential must agree to use effective contraception for the duration of the study and for 10 days prior and 30 days after the study
- F. Negative pregnancy test in women of childbearing age

Exclusion criteria:

- A. MELD score >22
- B. WBC count <1000 cells/mm3
- C. Platelet count < 25,000/mm3
- D. TIPS in place for less than a month
- E. Currently on antibiotics apart from rifaximin
- F. Infection at the time of the FMT (diagnosed by blood culture positivity, urinalysis, paracentesis as needed)

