Group 1: Oral and enema FMT, Group 2: Oral FMT+ enema placebo, Group 3: Oral placebo + enema FMT, Group 4: Both placebo *Visit 2* After re-confirming eligibility, the patient will be seen within 3±5 days of visit 1. Vital signs and weight will be measured. Targeted physical exam will be done based on any symptoms.

Their symptom diaries and dietary recall will be examined. Stool, blood and urine will be collected and processed (see section below), including urine

pregnancy testing for women of child-bearing potential. After this we will administer the assigned intervention by enema and oral capsules. This has been tolerated without any issues in our current protocols. These will be dispensed from our VAMC Investigational Pharmacy, which has been handling these for our prior and current FMT trials. The

following will be recorded in all FMTs (dose, Unit ID/Lot# of each treatment, Expiration Date and storage condition) The patient will be observed for a further 1 hour and then given another stool kit to bring back 10±5 days from this visit (Visit 3). All subjects will be given contact information for the study team to call in case any issues arise.

Optionally, subjects may elect to combine Visits 1 and 2 to minimize potential COVID exposure. In this case, stool collection kit would be mailed to subject before visit, and the staff would provide further instructions to subject on their use. The subject may determine whether he/she will collect a stool sample to bring to the study clinic visit. In the event the subject decides not to participate in the study, the stool collection kit would be discarded.

Visit 3: We will see the patient in the McGuire VAMC at day 15, at which point, dietary recall will again be performed along with changes in GI or other adverse events using interview and review of the symptom diaries. If no adverse event (AE) or serious adverse events (SAE) occur (standard definitions and in the human subjects protection section per FDA specifications), the subject will continue in the study. Vital signs and weight will be measured. Targeted physical exam will be done based on any symptoms. The stool sample, blood and urine will be collected for microbiota and safety analysis. Changes in blood counts that prompt attention (MELD score increase by 8, WBC count change to >13,000 or <2,000) will be monitored. If all is well, then subjects will be discharged with another stool kit and instructions for the last visit 15±3 days later (visit 4).

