3. The following will be recorded in all interventions (dose, Unit ID/Lot# of each treatment, Expiration Date and storage condition)

Number of interventions: One administration of rectal placebo or FMT and two administrations of oral FMT or placebo

We will ensure that each subject receiving active FMT will receive material (oral/rectal) from the same donor.

Duration of Follow-up after FMT: 6 months

Samples collected at baseline (before FMT), and at the visits specified above will be:

- a. Stool (microbiome, bile acid profile, metagenomics, metabolomics)
- Blood (CBC, Basic metabolic panel, LFTs, INR, endotoxin, and storage for circulating microbiome, systemic inflammatory markers, bile acids and metabolomics)
- c. Urine for metabolomics

Sample processing will be done using standard precautions at the McGuire VA Medical Center and samples will be stored for analysis of the secondary endpoints. Microbiota analysis will be performed at George Mason University and University of Minnesota, and metabolomics will be performed at the UC Davis NIH West Coast Metabolomics Center or Metabolon. We will perform the bile acid analysis at the McGuire VA Medical Center laboratories. Additional analyses at the Institute of Hepatology, London, UK, and the University of North Carolina at Chapel Hill. We may also use other referral laboratories as needed.

Statistical analysis: These will be performed using ANOVA of delta changes after intervention/follow-up using Chi-square and Fisher exact for non-parametric (hospitalizations, HE episodes, covert hepatic encephalopathy etc.), for continuous variables, and specialized bio-informatics analyses for the microbiota (see details below). These will be adjusted for age, gender, MELD score and alcoholic etiology of cirrhosis.

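### Secondary aim 1a stops counting adverse events on the planned day of the second dose, so it leaves out the period after repeat dosing

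*Combined protocol and SAP*

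**What the plan says.** The Overall objective makes a second oral capsule administration part of what the trial evaluates. Under Intervention, dosing is at baseline and day 30. Groups 1 and 2 repeat active capsules and Groups 3 and 4 repeat placebo. The Visit 4 text allows dose 2 to slip to day 45 after an unrelated infection and still counts it as the second dose.

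Against that timetable, secondary aim 1a reads "Frequency, severity and relatedness of solicited and unsolicited AEs through day 30". Its neighbour 1b and secondary aim 4 both run to six months.

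AE collection does not stop at day 30. The list of solicited AEs applies to the whole trial, Monitoring of Adverse Events describes monthly review to 6 months, and subjects withdrawn early are still followed to 6 months for safety.

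On blood sampling, subjects are "followed monthly in person, or by phone or videoconference at Months 3, 4, 5", and for remote visits "Mail-in kits for collection of stool, and urine will be provided along with instructions for use if visit is performed remotely". One month after dose 2 the text names other assessments: "We will also perform the cognitive tests and QOL assessment at one month post-second intervention and at 6 months". The sampling list opens "Samples collected at baseline (before FMT), and at the visits specified above will be" and includes "Blood (CBC, Basic metabolic panel, LFTs, INR, endotoxin, and storage for circulating microbiome, systemic inflammatory markers, bile acids and metabolomics".

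**The concern.** Repeat dosing is one of the features that the trial sets out to study, and the all-AE comparison is where a reader would look for its tolerability. A table built literally to aim 1a would describe dose 1 only. Events in the weeks after the second active dose would be in the database but outside the one aim that asks how often they occurred, how severe they were and whether they were related.

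A window chosen after the data are seen is also weaker evidence than one fixed beforehand. If the sponsor later wants to describe tolerability after dose 2, the choice of 30, 60 or 180 days would be open.

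**Working it through.** The plan gives no figure to reproduce here. The check is day arithmetic on the stated schedule, followed by a comparison of the sections that deal with AEs.

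**Inputs**
- Dose 1 on day 0, dose 2 on day 30 (Intervention, timing of administration).
- Latest dose 2: day 45 (Visit 4).
- Visit 3 on day 15, then "instructions for the last visit 15±3 days later (visit 4"), so Visit 4 falls between 15 + 12 = day 27 and 15 + 18 = day 33.
- Close of the aim 1a window: day 30 (Secondary aims).
- 25 subjects per group (Sample size), so 2 × 25 = 50 are planned for active dose 2.

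**Coverage after dose 2.** With D the day of dose 2, the days of follow-up inside aim 1a are max(0, 30 − D). With a window through day 75 they are 75 − D.

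| D | Aim 1a as written | Window through day 75 |
|---|---|---|
| 27 | 3 | 48 |
| 30 (planned) | 0 | 45 |
| 33 | 0 (closes 3 days before) | 42 |
| 45 (latest) | 0 (closes 15 days before) | 30 |

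Counting day 30 inclusively adds at most the dosing day itself. The table takes Visit 3 at its stated day 15. The Visit 2 text also gives 10±5 days for that visit. Read literally, this would allow Visit 4 on day 5 + 12 = 17 and leave 30 − 17 = 13 days, but that conflicts with dosing on day 30.

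Day 75 is the shortest fixed window that gives 30 days after the latest permitted dose: 45 + 30 = 75.

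**Does another section already fill the gap?**
- Aim 1b: six months, but only for potentially transmitted infections.
- Aims 1c and 4: new or worsening chronic conditions only.
- Secondary endpoint 1: six months, but limited to liver-related hospitalisations, serious events and AEs related to the interventions.
- Safety and hospitalization analysis: non-serious AEs are compiled to look for trends between groups, with no window or measure given.
- The closing sentence of the Adjudication paragraph, and the sentence after the solicited AEs: general statements that outcomes and safety assessments are compared between groups, again with no window.

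None of these fixes a period for comparing the frequency and severity of all AEs after dose 2.

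**The case against.** The strongest reply is that aim 1a is one sub-item and not the whole AE analysis. Solicited AEs are recorded throughout, graded on a chart, compiled by group and compared with placebo, and a six-month endpoint covers intervention-related AEs. The protocol also deliberately places intensive follow-up in the first 30 days. Dose 2 is the same five capsules without an enema, from the same donor, so lighter follow-up can be defended.

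Much of this stands. No AE data are lost, and it would be wrong to infer that AEs go uncollected or uncompared after day 30. How intensively to follow subjects is the sponsor's choice. But the general sentences set neither a period nor a measure, and a choice about visit intensity does not explain closing the all-AE comparison on the day of re-exposure.

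A reader might also infer that laboratory safety lapses for months after dose 2. After dose 1 there is a day-15 draw with named triggers ("Changes in blood counts that prompt attention (MELD score increase by 8, WBC count change to >13,000 or <2,000) will be monitored"), the last-visit wording is attached to Visit 4, and remote kits cover stool and urine only. The documents do not support that inference:
- The remote option is named for Months 3, 4 and 5, and in-person visits remain possible then.
- Samples are taken at clinic visits, and the sampling list includes the safety panel at the specified visits. Blood one month after dose 2 is therefore implied, though not written out.
- The end-of-study visit collects serum.
- The individual halting rules, the grading chart and the Laboratory section set limits for MELD, white cells and liver enzymes that are not tied to a visit. Subjects with AEs also get relevant laboratory tests.
- Figure 1 is not shown in the available text and may hold the blood schedule.

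**Conclusion.** The concern holds for the AE window alone. On the planned schedule aim 1a includes 0 days after dose 2, at most 3 if Visit 4 is at the early end of its window around day 30, and it closes up to 15 days before a delayed dose. This affects how AEs are described in all four arms, including the 50 subjects planned for active repeat dosing. It does not touch the six-month primary endpoint of FMT-related serious events.

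The conclusion assumes that day 30 in aim 1a is counted from the first dose, as it is in the dosing schedule. It is a low-cost improvement to a secondary aim, not a flaw that threatens the trial. The laboratory question is a matter of wording only.

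**What to change.** **Main change.** Reword aim 1a to run through day 75 from first dosing for every randomised subject, whether or not dose 2 was given, and report events with onset through day 30 as a separate row. The window should not be restricted to those who received dose 2. The Visit 4 text withholds it after refusal, transplant, death or hospice, an FMT-related infection or serious event, or during antibiotic treatment, so such a restriction would select on outcome and upset the comparison of arms.

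**Cost.** One edit under Secondary aims and one extra table row. The AE data are already to be collected; the change assumes that onset dates are recorded. The visit text does not mention symptom diaries after Visit 4, so the later period should be compared between arms, not with the first 30 days.

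**Clarification.** State in the follow-up text that the safety panel (CBC, metabolic panel, LFTs, INR) is drawn at the assessment one month after dose 2 and at Month 6. If the sampling list or Figure 1 already provides for this, only confirming words are needed.
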